4.2.6 Other secondary endpoints

Annualised rates for supporting exacerbation endpoints will be summarised and analysed as described in [Section 4.2.4.3](#).

Other binary endpoints will be summarised descriptively and analysed using a logistic regression model with factors which will include treatment, region and age (adolescents or adults). Baseline of the corresponding endpoint will also be included in the model (where relevant) as a continuous linear covariate. For the binary endpoints defined using absence of exacerbations, the logistic regression model will also include a factor for history of exacerbations (≤ 2 or > 2 in previous 12 months), similarly to the primary analysis in [Section 4.2.4.1](#).

The proportion of subjects who had no asthma exacerbations during the planned treatment period will be summarised descriptively by:

- Exacerbations in the year before study: ≤ 2 exacerbations, > 2 exacerbations
- Baseline eosinophils group: $< 300/\mu\text{L}$, $\geq 300/\mu\text{L}$

A similar logistic regression model will be fitted, for each of these two variables in turn, to this endpoint as above, with additional factors for the subgroup (where not already included)

and the treatment by subgroup interaction. This model will be used to estimate the treatment effect and its 95% CI within each of the subgroup categories.

Other continuous endpoints will be summarised descriptively and analysed using an MMRM model under a MAR assumption analogous to that specified for key secondary endpoints in [Section 4.2.5.1](#). All continuous secondary endpoints will be assumed a priori to meet the distributional assumptions without transformation. However, this will be evaluated during blinded data reviews, and if necessary the SAP will be updated to specify an appropriate transformation for any endpoint where this assumption is not reasonable.

The following is proposed for the continuous other secondary endpoints:

- Change from baseline in pre-BD FEF_{25-75%} analysed using MMRM and summarised descriptively; other pre-BD clinic visit spirometry only summarised descriptively.
- Change from baseline in biomarkers (clinic visit FENO, eosinophils (10⁹/L and Cells/ μ L) and total serum IgE (mg/L and IU/mL)) analysed using MMRM and summarised descriptively. These summaries and analyses will be repeated for the age subgroups at study entry: adults (≥ 65), adults (≥ 18 to < 65) and adolescents (≥ 12 to < 18). Eosinophil (10⁹/L) and total serum IgE (mg/L) data will also be included in the summaries of laboratory data.
- Change from baseline in weekly mean total daily asthma symptom score analysed using MMRM and summarised descriptively; weekly mean daytime and night-time asthma symptom scores only summarised descriptively.
- Change from baseline in weekly mean daily rescue medication use, night-time awakenings, morning home-based PEF and evening home-based PEF analysed using MMRM; any other eDiary variables only summarised descriptively.
- All HRU items defined in [Section 3.2.4.5](#) only summarised descriptively.
- All WPAI+CIQ scores defined in [Section 3.2.4.6](#) only summarised descriptively.
- Change from baseline in EQ-5D-5L VAS and health state valuation index analysed using MMRM; other EQ-5D-5L dimensions only summarised descriptively.
- CGI-C, PGI-C and PGI-S only summarised descriptively.

Time to first asthma exacerbation will be summarised using Kaplan-Meier estimates, and analysed using a Cox proportional hazards model with factors for treatment, region, age (adolescents or adults), and history of exacerbations (≤ 2 or > 2 in previous 12 months). This analysis will only be done on the planned treatment period (with censoring at the end of the time at risk as defined in [Section 3.2.1](#), for subjects without the event).

The proportional hazards assumption will be checked. If needed, further consideration will be given to models which make less restrictive assumptions, including (but not necessarily limited to):

- Stratified proportional hazards model
- Models which assume proportional hazards over shorter piecewise time intervals.

Time to first asthma exacerbation due to hospitalisations or ER visits (only) will be analysed similarly to time to first asthma exacerbation for any reason above.

Time to first asthma exacerbation (all types) will also be summarised using Kaplan-Meier estimates separately for subjects within each baseline eosinophils group (<300/ μ L and \geq 300/ μ L only).

A similar Cox proportional hazards model will be fitted to this endpoint as above, with additional factors for the subgroup and the treatment by subgroup interaction. This model will be used to estimate the treatment effect and its 95% CI within each of the subgroup categories.

A figure will be produced to summarise the cumulative number of asthma exacerbations over time.

Sensitivity and subgroup analyses will not be performed on other secondary endpoints, except where specified above.

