1.1.3 Other secondary objectives

Objective:	Endpoint/variable:
To assess the effect of 210 mg tezepelumab SC Q4W on other endpoints associated with asthma exacerbations	
Outcome variable: Time to first asthma exacerbation
 
Outcome measure: Asthma exacerbation hazard ratio vs placebo over 52 weeks
 
Outcome variable: Proportion of subjects who did not experience an asthma exacerbation over 52 weeks
 
Outcome measure: Difference in proportions vs placebo at Week 52
 
Outcome variable: Annualised rate of exacerbations associated with emergency room visit or hospitalisation
 
Outcome measure: AAER ratio vs placebo over 52 weeks

Objective:	Endpoint/variable:
To assess the effect of 210 mg tezepelumab SC Q4W on biomarkers	
Outcome variables: Change from baseline in
 
• Clinic based fractional exhaled nitric oxide FENO (ppb)• peripheral blood eosinophils• total serum IgE 
Outcome measure: Mean difference vs placebo at Week 52

To assess the effect of 210 mg of tezepelumab SC Q4W on other asthma control metrics	
Outcome variables: Change from baseline in
 
• weekly mean rescue medication use• weekly mean morning and evening home-based peak expiratory flow (PEF)• weekly mean number of night-time awakenings 
Outcome measure: Mean difference vs placebo at Week 52
 
Further details clarifying the definitions of these endpoints are given in Section 3.2.4.3 and Section 3.2.4.4.

Objective:	Endpoint/variable:
To assess the effect of 210 mg tezepelumab SC Q4W compared with placebo on health resource utilization and productivity loss due to asthma	
Outcome variables:
 
 • Asthma specific resource utilization (e.g. unscheduled physician visits, unscheduled phone calls to physicians, use of other asthma medications) • Work Productivity and Activity Impairment (WPAI+CIQ) Questionnaire and Classroom Impairment Questionnaire score 
Outcome measures:
 
 • Difference in number of asthma specific resource utilizations vs placebo over 52 weeks • Difference in WPAI+CIQ score vs placebo at Week 52
To evaluate the pharmacokinetics (PK) and immunogenicity of tezepelumab	
PK: Serum concentrations Immunogenicity: Incidence of anti-drug antibodies

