3.2.4.5 Health resource utilisation

Health care resource utilisation due to asthma will be recorded in the “Asthma-Related Events since Previous Visit” module of the eCRF.

Planned treatment period number of days/times and on-study number of days/times will be calculated for each subject for the following variables:

- Ambulance transport
- Hospitalisation
- Intensive care (days in intensive care)

- General care (days in general care)
- Emergency room visit
- Hospital admission or emergency department > 24 hours
- Visit to specialist
- Visit to primary health care physician
- Other health care visit
- Home visit, physician
- Home visit, other health care
- Telephone call, physician
- Telephone call, nurse
- Telephone call, other physician/health care provider
- Spirometry
- Advanced pulmonary function test
- Plain chest X-ray
- Computer tomography
- Oxygen initiated

The planned treatment period number per subject will be determined as:

Planned treatment period number = Sum of 'number of times/days' as entered on the eCRF page up to Week 52.

The on-study number per subject will be determined as:

On-study number = Sum of 'number of times/days' as entered on the eCRF page up to Week 64.

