3.2.4.6 Work productivity and activity impairment

The WPAI+CIQ questionnaire is a 10-item questionnaire that assesses productivity and activity impairment over the previous week.

There are a maximum of 10 questions and a minimum of 3 questions that will be completed by subjects as follows:

1. Currently employed (yes/no)
2. Hours missed work due to health problems
3. Hours missed work due to other reasons
4. Hours actually worked
5. Degree health affected productivity while working (0-10 scale, with 0 meaning no effect)
6. Attends class in an academic setting (yes/no)
7. Hours missed class due to health problems
8. Hours actually attended class
9. Degree health affected productivity while attending class (0-10 scale, with 0 meaning no effect)
10. Degree health affected regular activities (other than work or class) (0-10 scale, with 0 meaning no effect)

If the answer to question 1 is 'No, not currently employed', then the subject should skip to question 6. If the answer to question 6 is 'No, not currently attending class', then the subject should skip to question 10.

The WPAI+CIQ provide 4 scores:

- Absenteeism (work or class time missed)
- Presenteeism (impairment at work or class/reduced on-the-job effectiveness)
- Work productivity loss (overall work or class impairment/absenteeism plus presenteeism)
- Activity impairment

WPAI+CIQ outcomes are expressed as impairment percentages, with higher numbers indicating greater impairment and less productivity.

For each time point at which the WPAI-CIQ is administered, the following descriptive

statistics (if applicable) (n, total number of hours, mean per subject, standard deviation (SD), median, minimum and maximum) will be reported for those who are employed:

- # employed
- % of all subjects employed
- # of work hours missed due to asthma
- Absenteeism due to asthma
- Presenteeism due to asthma
- Work Productivity Loss
- Activity impairment

The following formulae will be used to calculate each of the outcome measures listed above:

- # currently employed – Yes in response to Question 1
- # of hours missed due to asthma – as responded in Question 2
- Absenteeism = $Q2/(Q2+Q4)$
- Presenteeism = $Q5/10$
- Work Productivity Loss = $Q2/(Q2+Q4)+[(1-Q2/(Q2+Q4))x(Q5/10)]$
- Activity Impairment = $Q10/10$

Similarly, the following will be reported for those subjects who are in school:

- # in school
- % of all subjects in school
- # of class hours missed
- Absenteeism due to asthma

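### Resource use and WPAI+CIQ have a difference versus placebo as their stated measure, but only descriptive summaries are planned, and the Week 52 resource totals are not adjusted for follow-up time

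*SAP*

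**What the plan says.** SAP 1.1.3 and protocol Table 3 set a secondary objective on resource use and productivity loss compared with placebo. The outcome measures are "Difference in number of asthma specific resource utilizations vs placebo over 52 weeks" and "Difference in WPAI+CIQ score vs placebo at Week 52".

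SAP 4.2.6 gives other continuous secondary endpoints an MMRM by default and then lists how each will be handled. The entries beginning "All HRU items defined in" (Section 3.2.4.5) and "All WPAI+CIQ scores defined in" (Section 3.2.4.6) assign these endpoints to descriptive summary only.

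SAP 3.2.4.5 derives resource use as a plain sum per subject: "Planned treatment period number = Sum of" the times or days "as entered on the eCRF page up to Week 52". A second, on-study sum runs "as entered on the eCRF page up to Week 64". Neither has a denominator or offset. For WPAI+CIQ, SAP 3.2.4.6 says that descriptive "statistics (if applicable) (n, total number of hours, mean per subject, standard deviation (SD), median, minimum and maximum) will be reported" at each time point. A contrast with placebo is not among them.

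Protocol 9.4.3.3 says that other continuous endpoints are both summarised and analysed by MMRM, and that other relevant annual rates get a model like the primary one. Further model details are left to the SAP. SAP Section 1 promises that changes from the protocol appear in Section 6, which does not mention this one.

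**The concern.** A measure defined as a difference versus placebo calls for an estimate of that difference and some statement of its precision. The plan provides neither for these two endpoints. A reader of the study report would have to subtract one arm's summary from the other's, without adjustment for the stratification factors or baseline.

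For resource use, the quantities being subtracted would be totals from subjects with different lengths of observation. The SAP adjusts for this elsewhere: a log time-at-risk offset for exacerbations (4.2.4.1), and exposure- and study-adjusted rates for adverse events (3.3.2). At stake is whether a protocol-specified secondary measure is estimated at all, and whether the resource figures can be read as annual use.

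**Working it through.** **Stated measure against planned analysis.** The placebo contrasts in SAP 1.1.3 compare as follows:

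| Endpoint | Stated measure | Planned analysis (SAP 4.2.4.4, 4.2.6) |
|---|---|---|
| Time to first exacerbation | Hazard ratio | Cox model |
| Exacerbation-free proportion | Difference in proportions | Logistic regression |
| Exacerbations with ER visit or hospitalisation | Rate ratio | Negative binomial |
| Biomarkers, rescue use, awakenings, PEF, EQ-5D-5L | Mean difference | MMRM (for EQ-5D-5L, VAS and index) |
| PGI-C, PGI-S, CGI-C | Proportions of responses | Descriptive |
| Resource use | Difference in number | Descriptive |
| WPAI+CIQ | Difference in score | Descriptive |

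The global impression scales are also descriptive only, but their stated measure is a proportion, so the two agree. Only the last two rows state a contrast and plan no between-group analysis.

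**Size of the follow-up effect.** The documents give no power or effect figure for these endpoints, so there is none to reproduce. The one usable input is the dropout assumption in protocol 9.2 and SAP 1.3: 10%, uniform over the study. With dropout proportion d uniform over the year, mean follow-up is 1 - d/2, which is 0.95 year (49.4 weeks) at d = 0.10.

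That reading agrees with the plan's own power for the subgroup with eosinophils below 300/µL. The variance term is (1/0.95)(1/0.6 + 1/0.3) + 2 × 2.4 = 10.06. Power is then Φ(√265 × ln 2 / √10.06 - 1.96) = Φ(1.60), about 94.5%, against the stated 94%.

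The expected raw total per subject is the annual rate times mean follow-up. This assumes a constant rate and no resource data after dropout.

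- Equal 10% dropout: each arm's total is 0.95 of the annual figure, so about 5% low. The ratio is unchanged. A difference shrinks in proportion: with assumed rates of 1.0 (placebo) and 0.5 (tezepelumab), -0.50 becomes 0.475 - 0.95 = -0.475.
- Unequal dropout (assumed, since the documents give no rates by arm), with a true rate ratio of 1.00:

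| Dropout, placebo / tezepelumab | Mean follow-up (years) | Ratio of raw totals, tezepelumab/placebo |
|---|---|---|
| 12% / 8% | 0.94 / 0.96 | 1.02 |
| 15% / 5% | 0.925 / 0.975 | 1.05 |
| 20% / 5% | 0.90 / 0.975 | 1.08 |
| 5% / 20% | 0.975 / 0.90 | 0.92 |

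Over arm-specific dropout of 5% to 20%, the ratio is off by about -8% to +8%, in either direction. A rate per subject-year, or a model with a log follow-up offset, removes this factor under the same assumptions.

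**The case against.** The strongest reply is that the important resource events are already modelled. SAP 4.2.4.4 analyses exacerbations with an ER visit or hospitalisation, and with hospitalisation alone, by a negative binomial model like the primary, with adjudicated versions. SAP 4.2.6 adds a Cox model for time to the first such event. This stands. What remains unmodelled is chiefly physician visits, telephone calls, ambulance use, tests and WPAI+CIQ.

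Second, stopping treatment does not end data collection. Subjects are encouraged to continue to Week 52, and protocol 7.1.1 names health care utilisation as key information in the telephone contacts under follow-up options 2 and 3. This also stands: truncation mainly affects study withdrawals.

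Third, descriptive reporting is defensible for the work and class scores. They are reported only for subjects employed or in school. That status is asked at each administration and can change after randomisation, so a model would compare selected subsets. This stands too.

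Fourth, protocol 9.4.3.3 leaves model details to the SAP, and protocol 8.9 allows health-economic analyses to be reported outside the study report. This stands only in part. Dropping the comparison is more than a model detail, and the stated outcome measure was left as a contrast.

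Finally, n, mean and SD by arm would let a reader form a crude difference and interval, so the information is not wholly absent. A planned, adjusted estimate would still be better.

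**Conclusion.** The mismatch is real and minor. Two other secondary outcome measures are worded as differences versus placebo, no estimate or interval is planned for either, and Section 6 is silent. The text alone establishes this; it needs no numerical assumption.

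The follow-up point is smaller. The shortfall of about 5% per arm rests on the stated 10% uniform dropout, a constant rate and no data after dropout. The -8% to +8% range for the ratio rests on assumed dropout by arm.

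A reader might infer more, and the documents do not support it:

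- That the resource comparison is biased in a known direction. One dropout rate is given, with no split by arm, so neither sign nor size is known.
- That the Week 64 sum distorts the comparison. It does mix extension entrants with subjects followed to Week 64, but the stated measure is over 52 weeks and the Week 52 sum is derived separately.
- That a trial claim is at risk. Both endpoints lie outside the testing procedure in SAP 4.1.2.

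**What to change.** In the SAP:

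1. **Resource use.** Report Week 52 counts per subject-year by arm. For the commoner items not already modelled, such as specialist visits, primary care visits and telephone calls, fit the planned negative binomial model with log follow-up time as offset. Define follow-up as randomisation to the last resource-use assessment, no later than Week 52. Do not subtract exacerbation days as the primary time at risk does, because resource use can occur during an exacerbation.
2. **WPAI+CIQ.** Analyse change from baseline in activity impairment, the one score that all subjects answer, with the planned MMRM at Weeks 24 and 52, the scheduled post-baseline visits.
3. **Reporting.** Give the ratio or difference versus placebo with a nominal 95% CI, labelled as outside the testing hierarchy.
4. **Wording.** Keep rare resource items and the work and class productivity scores descriptive, restate their outcome measures in SAP 1.1.3 to match, and record the change in Section 6.

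The cost is SAP wording and a few extra model runs on data already collected. The downside is a few more nominal intervals, which should not be read as tests.

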4.2.7 Exploratory endpoints

CCI [REDACTED]

[REDACTED]

[REDACTED]

[REDACTED]

[REDACTED]

[REDACTED]

[REDACTED]

[REDACTED]

- CCI [redacted]
 - | [redacted]
 - [redacted]
 - [redacted]
 - [redacted]
 - | [redacted]
 - | [redacted]
 - | [redacted]
 - [redacted]
 - [redacted]
 - | [redacted]
 - | [redacted]
 - [redacted]
 - [redacted]

CCI

4.2.8 Safety and tolerability

All safety variables will be summarised using the safety analysis set (see [Section 2.1.2](#) for details).

4.2.8.1 Adverse events

AEs will be summarised separately for the on-treatment and on-study periods as defined in [Section 3.1.4](#) unless stated otherwise. All AE summaries will be presented by treatment group. AEs occurring during the screening/run-in period, or occurring post-treatment will be listed, but not summarised separately.

An overall summary table will be produced showing the number and percentage of subjects with at least one AE in each of the following categories: any AEs, serious adverse events (SAEs), AEs with a fatal outcome, AEs leading to discontinuation of IP (DAEs), and adverse events of special interest (AESIs). The total number of AEs in the different AE categories will also be presented as well as the number of subjects (i.e. accounting for multiple occurrences of the same event in a subject).

All AEs will be summarised by system organ class (SOC) and preferred term (PT) assigned to the event using the MedDRA dictionary. For each PT, the number and percentage of subjects reporting at least one occurrence of the event will be presented (i.e. subjects with multiple occurrences of the same PT will only be counted once).

Similar summaries by SOC and PT will also be presented for:

- SAEs
- Fatal AEs
- DAEs
- DAEs causally related to IP
- SAEs leading to discontinuation of IP

- Each AESI category separately
- The most common AEs (defined as those occurring in >3% of subjects in either treatment group) – by PT only

All AEs (by PT) will be summarised additionally by causality and maximum intensity. If a subject reports multiple occurrences within each SOC and PT, the maximum intensity will be taken as the highest recorded (the order being mild, moderate and severe) respectively.

In addition, each AESI category will be summarised by causality.

The AESI of injection site reactions will be further summarised by:

- Site of injection (arm, thigh, abdominal wall)
- Total number of doses administered (1, 2, ..., 13), irrespective of timing of the injection site reaction event.

Exposure-adjusted AE summaries will be presented by SOC and PT for each of the following (on-treatment summaries only):

- All AEs
- Each AESI separately

In these summaries, the exposure-adjusted rate will be defined for each treatment as the number of subjects in that treatment group reporting the AE divided by the total time at risk for all subjects in that treatment group, the latter as defined in [Section 3.3.2](#). Rates will be reported as events per 100 subject-years.

Events confirmed by the independent adjudication committee (major adverse cardiac events (MACE) and malignancies) will be summarised by treatment.

The following AE summaries will be produced by treatment group and age category (adults (≥ 65), adults (≥ 18 to < 65) and adolescents (≥ 12 to < 18)):

- Overall summary table as described above, for the on-treatment and on-study periods.
- The most common AEs (defined as those occurring in >3% of subjects in either treatment group), by PT, for the on-treatment and on-study periods.
- AEs summarised by SOC and PT, for the on-treatment and on-study periods.
- SAEs summarised by SOC and PT, for the on-treatment and on-study periods.
- AEs summarised by PT and maximum intensity.

- DAEs summarised by SOC and PT.

